5. DEFINITIONS

SKAMP Total Score

The SKAMP total score will be the sum of the 13 individual item scores at each timepoint. Missing data will not be handled at an item level, if any of the 13 items are missing for a timepoint then the SKAMP total score will be missing for that timepoint.

Mean SKAMP Total Score

The mean SKAMP total score will be the average of all SKAMP total scores collected over the course of a laboratory assessment day, with the exception of the score from the session prior to dosing.

Onset of efficacy

The onset of efficacy, based on the SKAMP total scores, will be defined as the time of the first assessment time showing statistical significance between d-ATS and placebo. If no significant difference is found at any time point for the onset of efficacy, no onset of efficacy will be deemed to have occurred, and the onset of efficacy will be defined as 'none'.

Duration of efficacy

The duration of efficacy, based on the SKAMP total scores, will be defined as the difference between the time point that indicates that the effect has ended and the onset of efficacy, as defined above. The time point that indicates that the effect has ended will be defined as the first time point at which there is a non-significant difference between the two treatment groups after a time point in which there is a significant difference between the two treatment groups. If there is no time point at which there is a non-significant difference between the two treatment groups after a time point in which there is a significant difference between the two treatment groups, then the end of effect will be defined as 12 hours post-dose.

Onset of effect (50% reduction in SKAMP total score)

Onset of effect of 50% reduction in SKAMP total score is defined for each subject as the first time point at which there is a 50% reduction in SKAMP total score from the pre-dose observation on the same classroom day.

Duration of effect (50% reduction in SKAMP total score)

Duration of effect of 50% reduction in SKAMP total score will be determined by persistence of the 50% reduction from the pre-dose observation in SKAMP total score level. The end of effect will be determined as the first timepoint after onset of effect at which 50% reduction from the pre-dose observation in SKAMP total score is not observed. The duration of effect will be calculated as the difference between the end of effect and onset of effect, in hours.

Age

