<treatment*timepoint> 0 0 0 0 0 0 0 0 0 -1 0 0 0 0 0 0 0 0 0 0 1  
/ cl;
```

The two treatment levels will be: d-ATS (5, 10, 15, 20 mg doses combined) and placebo. Continuous summary statistics will be presented for the SKAMP total score at each time point for Visits 6 and 7 for the FAS population. Raw means, LS means, differences in LS means, and 95% CI for the difference between treatment arms, and p-values will be calculated for each post-dose time point and for mean score over the treatment day for the FAS population.

The SKAMP total scores will also be plotted by time point for the FAS population.

Scaled residual and random effects plots will be considered to check the assumptions behind the mixed model.

The assessment of treatment differences will follow the closed testing procedure described in Section 7. The closed testing procedure starts from the time-point of 1 hour post-morning dose, then 2, 3, 4.5, 6, 7, 9, 10 and 12 hours post-dose. At each timepoint the order of testing will be onset of efficacy followed by duration of efficacy, before moving to the next timepoint. Duration of efficacy will not be considered until onset of efficacy has been determined.

- The onset time of efficacy action will be determined as the first post-dose time where the difference between the two treatments is statistically significant (i.e., $p \leq 0.05$).
- If the difference between the two treatments is statistically significant (i.e., $p \leq 0.05$) at the 1 hours post-dose time point, the duration of efficacy will be claimed as the difference in hours between the end of efficacy; the last consecutive time point at which the difference is still statistically significant (i.e., $p \leq 0.05$) and onset of efficacy. If there is no time point at which there is a non-significant difference between the two treatment groups after a time point in which there is a significant difference between the two treatment groups, then the end of efficacy will be defined as 12 hours post-dose.

For example, if a statistically significant difference in mean SKAMP total scores for d-ATS vs. placebo was determined at 1 hour post-dose and statistical significance was measured at all time-points up to and including 10 hours post-dose, but statistical significance was not reached at 12 hours post-dose, onset of clinical efficacy and end of clinical efficacy would be defined as 1 hours post-dose and 10 hours post-dose, respectively, with duration of efficacy being 9 hours.

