Duration of effect for 50% reduction in SKAMP total score will be determined by persistence of the reduction of 50% from the pre-dose observation in SKAMP total score. The end of effect will be determined as the first timepoint after onset of effect at which the 50% reduction in SKAMP total score is not observed. The duration of effect will be calculated as the difference between the end of effect and onset of effect, in hours. Duration of effect will be analyzed using the same methodology as the onset of effect. Subjects that record a 50% reduction in the SKAMP total score from the baseline value such that duration of effect continues at their final assessment time for that classroom day will be censored at that time. Subjects without an onset of effect will be excluded from the analysis of duration of effect. A sensitivity analysis will be performed where subjects without an onset of effect will be imputed to have duration of effect of 0 hours.

Supportive analysis of onset of efficacy and duration of efficacy will be conducted using the same approach for the Completers population.

Once onset and duration of efficacy are estimated (using the MMRM approach analysis for the FAS, as described above), the sensitivity analysis will be conducted for primary variable as specified in section 7.1.1 by excluding data from time points before onset and after the last time point included into the duration of efficacy.

All data, including derived values, will be listed.

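### The window re-run of the primary analysis cannot test robustness, because its time points are chosen by significance in the same data

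*SAP*

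**What the plan says.** After onset and duration have been estimated, SAP 7.1.3.1 states that "the sensitivity analysis will be conducted for primary variable as specified in section 7.1.1", carried out "by excluding data from time points before onset and after the last time point included into the duration of efficacy". It bases this on the mixed-model results for the Full Analysis Set described earlier in the same section.

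That earlier text fixes both ends by p of 0.05 or less. Onset is "the first post-dose time where the difference between the two treatments is statistically significant". The end is "the last consecutive time point at which the difference is still statistically significant". SAP Section 5 defines onset in the same way, as "the time of the first assessment time showing statistical significance between d-ATS and placebo", but defines the end of effect differently: it "will be defined as the first time point at which there is a non-significant difference between the two treatment groups" following a significant one.

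Testing "starts from the time-point of 1 hour post-morning dose, then 2, 3, 4.5, 6, 7, 9, 10 and 12 hours post-dose", which makes nine post-dose times. The primary variable is "the average of all SKAMP total scores collected over the course of a laboratory assessment day", leaving out the pre-dose session. Because the re-run follows Section 7.1.1, it would produce an LS-mean difference, a 95% confidence interval and a p-value.

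**The concern.** A sensitivity analysis is useful only if it could have come out against the primary result. SAP 7.1.2 takes that view itself: it wants to see whether efficacy results hold up when assumptions change. Here the assumptions stay the same and the data are filtered on the outcome. Time points are selected for a significant treatment difference, and the difference is then re-estimated and re-tested on those same points with no allowance for the selection.

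At stake is how the output is read. A significant p-value, often with a larger estimate, would be labelled as support for the primary result while adding no independent evidence. The primary test itself does not depend on it.

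**Working it through.** **Inputs from the documents.** 74 completers, 80% power, two-sided 0.05 (SAP 3.1); nine post-dose times (SAP 7.1.3.1); onset and duration tested only if the primary has p < 0.05 (SAP 7).

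**The plan's own figure.** The 74 cannot be reproduced because the SD and the difference are redacted. Working backwards, the implied paired standardized difference is (1.960 + 0.842)/√74 = 2.802/8.602 = 0.326 (0.330 with the exact t).

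**The SAP's worked example.** Times 1 to 10 h are significant and 12 h is not. By the 7.1.3.1 rule the window runs from 1 to 10 h. Eight of nine times stay, 12 h is dropped because it was not significant, and duration is 10 − 1 = 9 h. By the Section 5 rule the effect ends at 12 h, duration is 12 − 1 = 11 h, and the non-significant 12 h time could stay in.

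**Why the re-run must be significant under 7.1.3.1.** Suppose k times are kept, all favouring the same treatment, each with difference d_j ≥ c·SE_j, where c is the critical value. Averaging gives mean(d) ≥ c·mean(SE_j). The SD of an average is never larger than the average of the SDs, so SE(mean) ≤ mean(SE_j). Hence mean(d)/SE(mean) ≥ c. This is exact for complete paired data. The refitted mixed model re-estimates its variance, so there it holds closely but not exactly.

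**Size, by simulation.** Assumptions: 74 subjects; nine paired differences per subject with SD 1; correlation between times 0.3 or 0.6; a paired t-test at each time in place of the mixed model. The primary gate is applied first. The window then runs from the first significant time to the last consecutive significant time. At least 10,000 trials were run per case. The ratio is the mean window estimate divided by the mean all-nine-times estimate in gated trials, so the effect of the gate itself cancels.

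| True effect | Ratio, corr. 0.3 | Ratio, corr. 0.6 |
|---|---|---|
| None | 1.72 | 1.31 |
| Flat 0.2 SD | 1.35 | 1.16 |
| Flat 0.25 SD | 1.24 | 1.12 |
| Flat 0.33 SD | 1.10 | 1.06 |
| Flat 0.6 SD or more | 1.00 | 1.00 |
| Hump, mean 0.33 SD | 1.34 | 1.31 |
| Slow rise* | 0.98 | 0.98 |

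*0.35, 0.30, 0.40, 0.50, 0.60, 0.60, 0.60, 0.50, 0.40 SD.

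- The re-run was significant in essentially 100% of trials that had a window, including trials with no true effect that passed the gate.
- Flat 0.33 SD: 0.363/0.331 = 1.10 and 0.361/0.342 = 1.06.
- Flat 0.6 SD: all nine times are kept in about 99% of trials, so nothing is selected.
- Hump at correlation 0.3: the window estimate is 0.445 against 0.332 for the whole day. The true effect in the kept windows averages 0.423 against 0.33. So 0.423 − 0.33 = 0.093 is a change of target, and 0.445 − 0.423 = 0.022 (about 5%) is selection.

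**Section 5 end rule instead.** If the first non-significant time is kept, the re-run with no true effect is still significant in 77–88% of gated trials. The ratio at flat 0.33 SD is about 1.00.

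**The case against.** A reader might infer that the estimate is inflated by construction and that this analysis can only make the drug look better. The documents do not support that. The window stops at the last consecutive significant time, so one early miss can discard later and larger effects. In the simulations the window estimate was below the all-day estimate in roughly 5–10% of trials at flat 0.25–0.33 SD, and in about 20% for the slow-rise profile. If all nine times are significant, nothing is dropped.

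A reader might also put the bias at about 30%, by setting a window estimate of about 0.32 against a true 0.25 SD (0.32/0.25 = 1.28). That mixes in the primary gate: among trials that pass it, the all-day estimate already averages about 0.26 (correlation 0.3) or 0.29 (0.6). The part due to the window is the 24% / 12% shown above.

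Four further points on the other side:

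- **The rule is not fully specified.** SAP 7.1.3.1 gives a duration rule only for the case where 1 h is significant, and SAP 7 stops testing at the first failure. Under that strict sequence the hump profile at mean 0.33 SD still gives a significant re-run in at least 99.9% of trials with a window, with ratios 0.426/0.398 = 1.07 and 0.477/0.448 = 1.06. The conclusion stands.
- **Section 5 may keep one non-significant time.** This is true and would remove most of the inflation. The wording of the re-run refers back to 7.1.3.1, so that rule is the more natural reading, but the conflict is real.
- **Part of any rise is not selection.** The primary model has ten time levels including pre-dose, while the defined endpoint excludes it. If the pre-dose difference is zero, dropping that level multiplies the model average by 10/9 = 1.11. That moves towards the defined endpoint.
- **Other robustness checks exist.** Multiple imputation, LOCF, worst-case and Completers analyses are all planned. This limits the harm and is accepted.

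**Conclusion.** The point holds, at minor severity. Under the SAP 7.1.3.1 rule the re-run's significance is practically guaranteed by how its window is chosen, so its p-value and confidence interval are not valid and it says nothing about robustness. That follows from the rule and does not depend on the simulated effect sizes.

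The size of the bias does depend on assumptions. It is about 24% / 12% at a flat 0.25 SD and about 10% / 6% at 0.33 SD, close to the effect implied by 74 completers (correlation 0.3 / 0.6). It is nil when all nine times are significant, and slightly negative on average for a slow rise. For a rise-and-fall profile most of the increase is a different target. SD, correlations and time profiles are all assumed, and paired t-tests stand in for the planned model, so no figure can be tied to this trial. The primary test and its type I error are not affected.

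**What to change.** Choose one of two changes in SAP 7.1.3.1:

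1. Keep the window but report only the mean difference within it, as a description. Give no p-value or confidence interval and drop the sensitivity label.
2. Replace it with a window fixed in advance from the design, for example 1–9 h while the patch is worn, with 10 and 12 h shown separately. Label this a supplementary estimand, because the primary endpoint covers all nine post-dose times.

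In either case, reconcile the end of effect in Section 5 (first non-significant time) with that in Section 7.1.3.1 (last consecutive significant time). If the first option is chosen, also say what is reported when onset is 'none'.

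The cost is a sentence or two of SAP text and no new data. SAP Section 1 already provides a change log and a final version before database lock.

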7.1.3.2 PERMP

Continuous summary statistics will be presented for PERMP-A and PERMP-C scores on the PERMP math test at screening and at each protocol-specified time point during the double blind period for the FAS. The PERMP-A and PERMP-C scores will also be plotted by time point for the FAS.

The number of items attempted and the number of items correct at each time point after dosing for Visits 6 and 7 will be analyzed in the same way as for the SKAMP primary efficacy analysis.

Raw means, LS means, differences in LS means, and 95% CI for the difference between treatment arms, p-values, and model results will be presented for each variable at each time point after dosing.

Change from pre-dose for PERMP-A and PERMP-C will be examined. Each post-dose PERMP-A and PERMP-C score will be analyzed by t-test on the change from pre-dose within group.

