Investigational Therapy:	
d-Amphetamine Transdermal Drug Delivery System (d-ATS) 9-hour patch (5 mg d-amphetamine /4.76 cm^2 patch).
 
d-Amphetamine Transdermal Drug Delivery System (d-ATS) 9-hour patch (10 mg d-amphetamine /9.52 cm^2 patch).
 
d-Amphetamine Transdermal Drug Delivery System (d-ATS) 9-hour patch (15 mg d-amphetamine /14.29 cm^2 patch).
 
d-Amphetamine Transdermal Drug Delivery System (d-ATS) 9-hour patch

Amendment 4: Version 5.0 May-08-2013

Amendment 3: Version 4.0 December-11-2012

Amendment 2: Version 3.0 October-31-2012

Amendment 1: Version 2.0 August-02-2012

Final Protocol May-25-2012

	(20 mg d-amphetamine /19.05 cm  patch).
Reference Therapy:	Placebo
Treatment Duration:	5 weeks of dose titration period and 2 weeks of double blind treatment period
Efficacy Assessments	
ADHD-RS-IV at Visit 0 (baseline; Day 0), Visit 1 (Day 7), Visit 2 (Day 14), Visit 3 (Day 21), Visit 4 (Day 28), Visit 5 (Day 35), Visit 6 (Day 42) and Visit 7 (Day 49).
 
SKAMP and PERMP will be collected as follows:
 
 
Visit -1 (Screening): Level finding math test and 1 PERMP at demonstrated level.
 
Visit 0 (baseline; Day 0): Two practice PERMPs at demonstrated level
 
Visit 1(Day 7), Visit 2 (Day 14), Visit 3 (Day 21) and Visit 4 (Day 28): One practice PERMP at demonstrated level
 
Visit 5 (Day 35): Half day practice classroom;(SKAMP and PERMP pre-dose and 1 and 2 hours post dose)
 
Visit 6 (Day 42) and Visit 7 (Day 49): PERMP and SKAMP within 30 minutes prior to dosing and at 1, 2, 3, 4.5 (4½), 6, 7, 9, 10, and 12 hours following administration of study drug.
 
Conners' Parent Rating Scale-Revised Short Form will be completed by parent/caregiver on the day before a clinic visit: on Day 6, Day 13, Day 20, Day 27, Day 34, Day 41, and Day 48.
 
Clinical Global Impression: CGI-S will be collected on Day 0 (pre-dose). CGI-I will be collected on Visit 1(Day 7), Visit 2 (Day 14), Visit 3 (Day 21), Visit 4 (Day 28), Visit 5 (Day 35), Visit 6 (Day 42) and Visit 7 (Day 49).
 

Safety Assessments ECG	
ECG assessments will be performed as follows:
 
 
Visit -1 (Screening)
 
Visit 0 (baseline; Day 0)
 
Visit 5 (Day 35), Visit 6 (Day 42), and Visit 7 (Day 49) or early termination (prior to discharge).
 

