#### 4 STUDY OBJECTIVES

Primary:

- To assess efficacy of d-ATS compared to placebo as measured by the SKAMP total score.
- To assess the safety of d-ATS

Amendment 4: Version 5.0 May-08-2013

Amendment 3: Version 4.0 December-11-2012

Amendment 2: Version 3.0 October-31-2012

Amendment 1: Version 2.0 August-02-2012

Final Protocol May-25-2012

Secondary:

- To assess onset of efficacy of d-ATS compared to placebo as measured by the SKAMP total score
- To assess duration of efficacy of d-ATS compared to placebo as measured by the SKAMP total score
- Additional efficacy assessments include the Permanent Product Measure of Performance (PERMP), the ADHD-RS-IV, Conners' Parent Rating Scale-Revised Short Form (CPRS-R:S) and the Clinical Global Impression (CGI) scale.
- To assess the skin irritation, discomfort, adhesion and adhesive residue of d-ATS

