2. STUDY OBJECTIVES

The primary objective is to assess efficacy of d-Amphetamine Transdermal Drug Delivery System (d-ATS) compared to placebo, as measured by the Swanson, Kotkin, Agler, M-Flynn and Pelham Scale (SKAMP) total score. An additional primary objective is to assess the safety and tolerability of d-ATS.

The secondary objectives are:

- To assess onset of efficacy of d-ATS compared to placebo as measured by the SKAMP total score
- To assess duration of efficacy of d-ATS compared to placebo as measured by the SKAMP total score
- To assess additional efficacy assessments including:
 - Permanent Product Measure of Performance (PERMP)
 - Attention-Deficit/Hyperactivity Disorder Rating Scale, Version IV (ADHD-RS-IV)
 - Conners' Parent Rating Scale-Revised Short Form (CPRS-R:S)
 - Clinical Global Impression (CGI) scale.
- To assess the skin irritation, discomfort, adhesion and adhesive residue of d-ATS

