7.1.1 Primary Variable

Data Summaries

Continuous summary statistics will be presented for the mean SKAMP total score for Visits 6 and 7 for the FAS. Similar summaries will be presented for the Completers population.

Primary Efficacy Analysis

A likelihood-based Mixed-effect Model Repeated Measures (MMRM) will be used to assess the primary objective.

In the model, the SKAMP total score for each timepoint will be analyzed with the fixed effects of sequence (two levels), period (two levels), treatment (two levels) and time (10 levels, one for each of 30 minutes prior and 1, 2, 3, 4.5, 6, 7, 9, 10, and 12 hours post dosing) while the repeated measures effect of timepoint will be defined for subject within sequence and ‘Variance Components (VC)’ covariance structure. An example of the SAS procedure to be used is presented below.

```
proc glimmix data=<dataset>;
  class <treatment sequence period timepoint subject>;
  model <SKAMP> = <treatment>
    <sequence>
    <period>
    <timepoint>
```

```
<treatment * timepoint>
/solution ddfm=kr;

random <timepoint> / type=vc subject=<subject * period> residual;
lsmeans <treatment> / pdiff cl alpha=0.05;

estimate 'd-ATS - Placebo' <treatment> -1 1 / cl;
run;
```

Note: *<italics>* identifies where actual variable name substitutions are required.

<sequence> will be required to be defined as <treatment * period> to ensure estimates are obtainable. The two treatment levels will be: d-ATS (5, 10, 15, 20 mg doses combined) and placebo. The treatment * time interaction is included in the model to allow the form of the relationship to be modeled. The purpose of including the interaction term is not to test it for significance and so p-value will not be presented. Raw means, least-squares (LS) means, differences in LS means, and 95% confidence interval (CI) for the difference between treatment arms, and p-values will be calculated for SKAMP total score over the treatment day for the FAS (primary), and Completers populations.

Scaled residual and random effects plots will be considered to check the assumptions behind the mixed model.

Assessment of Carryover

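### PERMP change from pre-dose is tested only by within-group t-tests, which have no comparator and are not labelled descriptive; the treatment comparison of the scores themselves is already planned

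*SAP*

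**What the plan says.** PERMP is a secondary efficacy measure. Protocol section 4 lists it among the secondary objectives ("Additional efficacy assessments include the Permanent Product Measure of Performance (PERMP"), and SAP section 2 does the same under "To assess additional efficacy assessments including". On each of the two classroom days it is collected ten times: "PERMP and SKAMP within 30 minutes prior to dosing and at 1, 2, 3, 4.5 (4½), 6, 7, 9, 10, and 12 hours" after dosing (Protocol synopsis, Efficacy Assessments).

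SAP 7.1.3.2 gives two inferential analyses for PERMP-A (problems attempted) and PERMP-C (problems correct).

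1. The post-dose scores at Visits 6 and 7 "will be analyzed in the same way as for the SKAMP primary efficacy analysis". That model, in SAP 7.1.1, has "fixed effects of sequence (two levels), period (two levels), treatment (two levels) and time (10 levels" in all), plus a treatment-by-timepoint interaction in the code, and a direct contrast, "estimate 'd-ATS - Placebo' <treatment> -1 1 / cl". For PERMP, "differences in LS means, and 95% CI for the difference between treatment arms, p-values, and model results will be presented for each variable" at every time point after dosing.
2. Change from pre-dose is also to be examined: "Each post-dose PERMP-A and PERMP-C score will be analyzed by t-test on the change from pre-dose within group".

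SAP section 5 defines baseline for change analyses in the crossover phase as the pre-dose value on the same classroom day. Protocol 8.2.2 specifies no PERMP analysis, so nothing there calls for the within-group tests.

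**The concern.** A t-test of change within one arm asks whether the score moved during the day, not whether it moved more on d-ATS than on placebo. Between the pre-dose test and a test up to 12 hours later, a child may tire, may perform differently by time of day, and may still be gaining from practice. Any of these shifts the mean change with no drug effect at all. A pattern of significant change on d-ATS and non-significant change on placebo is likewise no evidence that the two differ.

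The tests stand under secondary efficacy variables with no descriptive or exploratory label. Elsewhere the SAP does mark output as non-inferential: section 7.6 for the dermal data and section 7.7 for safety. Protocol 6.1 says PERMP is there to assess how long efficacy lasts relative to placebo. Hour-by-hour within-arm p-values invite a statement of that kind without answering that question. A reader who wants a PERMP result expressed as change from pre-dose would find only these p-values.

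**Working it through.** The documents state no sample size, power or alpha for PERMP, so there is no figure of the plan's own to reproduce. The check has two parts.

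**What each analysis estimates.** Write the expected change from pre-dose at time t as drift(t) on placebo and drift(t) + effect(t) on d-ATS, with drift common to both.

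- Within-group test on d-ATS: tests drift(t) + effect(t) = 0.
- Within-group test on placebo: tests drift(t) = 0.
- Between-treatment difference: [drift(t) + effect(t)] − drift(t) = effect(t).

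Only the third isolates the drug effect. In the planned model for the scores, common drift is absorbed by the time term and cancels from the d-ATS minus placebo contrast in the same way.

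**How often drift alone gives a significant within-arm result.** Inputs:

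- n = 74, the expected completers (SAP 3.1), and n = 90, the number randomized, as an upper case because PERMP is summarized for the FAS.
- Two-sided 0.05, the level used for SKAMP in SAP 3.1.
- Drift d of 0.1 to 0.5 SD of the change. This is an assumption, shown as a range; the documents give no value.
- Drug effect zero.

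The power of a one-sample t-test comes from the noncentral t distribution with n − 1 degrees of freedom and noncentrality d × √n. For d = 0.3 and n = 74, this is 0.3 × 8.602 = 2.58.

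| Assumed drift (SD of change) | Noncentrality, n = 74 | Significant, n = 74 | Significant, n = 90 |
|---|---|---|---|
| 0 | 0 | 5% | 5% |
| 0.1 | 0.86 | 13.6% | 15.5% |
| 0.2 | 1.72 | 39.7% | 46.7% |
| 0.3 | 2.58 | 72.1% | 80.4% |
| 0.5 | 4.30 | 98.9% | 99.7% |

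A simulation set the two kinds of test side by side: 20,000 two-period crossover trials, 37 children per sequence, the same drift under both treatments, no drug effect, and an assumed within-child correlation of 0.5. The between-treatment test compared period differences between sequences.

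| Drift (SD of change) | Within-arm test significant | Between-treatment test significant |
|---|---|---|
| 0 | 5.1% | 5.1% |
| 0.2 | 40.1% | 4.8% |
| 0.3 | 72.6% | 4.9% |
| 0.5 | 98.8% | 4.8% |

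Simulation error on a 5% rate is about 1.96 × √(0.05 × 0.95 / 20,000) = 0.3 percentage points, so the last column does not differ from nominal. The simulated comparison is a standard crossover test on the change. It is not the SAP's mixed model, and it says nothing about that model's covariance structure.

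**The case against.** The strongest reply is that the treatment comparison already exists. SAP 7.1.3.2 specifies it just before the t-tests, with differences, intervals and p-values at every post-dose time. The SAP attaches no efficacy claim or decision rule to the within-group tests. This stands, and it rules out a stronger reading: someone who saw only the t-test sentence might infer that PERMP is never compared between treatments, or that drift will be reported as drug effect. The documents support neither. Drift misleads only if the within-group p-values are taken as evidence of efficacy.

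Practice is also limited by design. SAP 4.2.2 provides a different test version at each assessment, and the Protocol synopsis schedules practice tests from screening to Visit 5. This stands for practice, but it does not remove fatigue or time of day.

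A reader might also count 9 times × 2 scores × 2 treatments = 36 tests and quote 1 − 0.95^36 = 84% as the chance of a false positive. That figure should not be used. It assumes independence, yet the nine changes in a day share one pre-dose value, both scores come from the same test, and the same children supply both arms. The count also takes group to mean treatment arm, which the sentence does not say. Nor is lack of multiplicity control peculiar to these tests: the closed procedure covers only SKAMP onset and duration, so the PERMP model p-values and the ADHD-RS-IV, CPRS-R:S and CGI-I tests lie outside it too.

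What remains is that a comparator-free test is specified as the sole inference on change from pre-dose, without a label.

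**Conclusion.** The point holds and is minor. The within-group t-tests cannot answer the question PERMP was included to answer, and the SAP does not say they are descriptive. The main PERMP comparison of d-ATS with placebo is unaffected. With no drug effect and 74 children, a common drift of 0.2 / 0.3 / 0.5 SD of the change gives a significant within-arm result about 40% / 72% / 99% of the time, against about 5% for a between-treatment comparison. Those rates depend on assumed drift sizes and describe one test at one time point; they do not predict what this trial will show. Drift could also run downward and mask a benefit within the d-ATS arm.

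**What to change.** In SAP 7.1.3.2, do one of the following:

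- delete the within-group t-tests; or
- replace them with the within-child d-ATS minus placebo difference in change from pre-dose at each post-dose time, with period in the model, reported as an estimate and 95% CI and labelled supportive to the planned model.

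In either case, show within-arm change as descriptive means only, and add that PERMP inference rests on the treatment contrast. The supportive label matters because the pre-dose score on a classroom day follows six home days on that week's treatment, so it is not a treatment-free baseline.

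The cost is one changed sentence and one table shell. No new data are needed.
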